6.1.7 Handling of Dropouts and Missing Data

There will be no imputation of missing data for efficacy endpoints.

Seizure Diaries:

Seizures are recorded in the Daily Seizure Diary (DSD), while the End of Day Diary (EDD) provides Yes/No confirmation that that seizures were experienced for a specific date, or that the date was seizure free.

- If no seizures are entered in the DSD and the EDD confirms seizure freedom, the number of seizures for that date is zero.
- If seizures are entered in the DSD and the EDD states seizure freedom, the seizures recorded for that date supersede the EDD stating seizure freedom.
- If no seizures are entered in the DSD and there is no response in the EDD, that day will be considered to have missing diary data.

- If no seizures are entered in the DSD and there is a Yes response in the EDD, that day will be considered to have missing diary data.

Unless specified otherwise in the relevant sections describing analyses for individual parameters, missing diary data will not be imputed for efficacy variables. Hence for subjects missing some of the daily measurements, the available data will be used. No explicit imputation will be performed for subjects who drop out prior to end of study (Visit 12).

Handling of missing date information for AEs:

- The term *missing date* refers to a completely missing date or to an incomplete date/partial date where parts are not available, e.g. missing month/day/year.
- Missing start and end dates will be imputed conservatively, i.e. missing values will be imputed in such a way that the duration of the AE is considered with the longest possible duration and such that, whenever the AE may potentially start after first IMP, the AE will be handled as a TEAE.
- The missing start date and End date of AE will be imputed for the purpose of calculating treatment emergent status and assigning events to treatment periods using definitions given in the following table.

Handling of missing date information for AEs:

- The term *missing date* refers to a completely missing date or to an incomplete date/partial date where parts are not available, e.g., missing month/day/year.
- Missing start and end dates will be imputed conservatively, i.e., missing values will be imputed in such a way that the duration of the AE is considered with the longest possible duration and such that, whenever the AE may potentially start after the first dose of IMP, the AE will be handled as a TEAE.
- The missing start date and end date of an AE will be imputed for the purpose of calculating treatment-emergent status and assigning events to treatment periods using the definitions given in the following table.

Adverse events

Partial /Missing Start Date	
Missing day – If the AE start day is missing but month and year are present, then impute the 1st of the month unless the month and year are the same as the first dose of study drug. If this is the case, then impute the day of the first dose.
 
Missing day and month – If the AE start day and month both are missing but year is present, then impute 1st January unless the year is the same as first dose date. If this is the case, then impute the day and month of the first dose.
 
Completely missing – Impute the first dose date unless the end date suggests it

-----------------------------	---

	
could have started prior to this date, in which case impute the 1st January of the same year as the end date.
 
When imputing a start date, ensure that the new imputed date is sensible, i.e., is prior to the end date of the AE.

Partial /Missing End Date	
Missing day – If the AE end date is missing but month and year are present, then impute the last day of the month, unless the year and month are the same as the first dose of study drug. If this is the case, then impute the date of the last dose.
 
Missing day and month – If the AE has missing day and month but year is present, then impute 31st December.
 
Completely Missing – Need to look at whether the AE is still ongoing before imputing a date and also when it started in relation to starting study drug. If the ongoing flag is missing, then assume that the AE is still present (i.e., do not impute a stop date). If the AE has stopped and the start date is prior to first dose date, then impute the first dose date. If the AE started on or after the first dose date, then impute an end date that is after the last dose date.

6.1.8 Conversion of time interval

In case a time interval was calculated in days and needs to be converted into weeks, months or years the following conversion factors need to be used:

1 week = 7 days

1 month = 30.4 days

1 year = 365.25 days

6.1.9 Pooling of Investigative Sites and Interaction of treatment by Site

The primary analysis will use data pooled across all investigative sites. Region (UK, US, Canada, France, Germany, Netherlands, Spain) and site differences may be explored in preliminary analyses depending on the number of subjects randomized by each site/region.

6.1.10 Determination of Sample Size

The sample size for Cohort 2 was estimated from the results of two randomized, placebo-controlled trials for the treatment of Dravet syndrome with stiripentol. The results from the two trials, STICLO France and STICLO Italy, were reported in the European Public Assessment Report (EPAR) for stiripentol ([EMA, 2007](#)). In the stiripentol groups, the standard deviation (SD) of the percentage change in seizure frequency from baseline to month 2 was 42% in the STICLO France trial and 26% in the STICLO Italy trial. The analogous SDs for placebo groups were 38% and 62%. For the current trial, an SD of 50% was assumed for the primary analysis comparing ZX008 to placebo on the change from baseline in seizure frequency. Using a two-sided test at the $\alpha=0.05$ significance level, a sample size of 35 subjects per treatment group affords 90% power to detect a difference in mean change from baseline of 40 percentage points.

In December 2016 results from a double-blind, placebo-controlled Phase 3 study with Epidiolex to treat seizures in Dravet syndrome were presented at the American Epilepsy Society Meeting (<http://ir.gwpharm.com/events.cfm>). In the Epidiolex study, active drug reduced seizures by 39% compared to a reduction of 13% in the placebo. Review of the data suggested that the standard deviation was relatively large, likely above 50% in both treatment groups. In consideration of this new data, the expected SD was increased to 55. Other assumptions in the sample size calculation have remained unchanged. A sample size of approximately 80 subjects (40 per arm) affords 90% power to detect a difference in mean change from baseline of 40 percentage points with 55% SD. Given the variability seen in the STICLO and Epidiolex trials, the sample size for the current trial was increased from 35 to 40 subjects per treatment arm for a total of 80 subjects.

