3.2 NUMBER OF SUBJECTS

Cohort 1: Approximately 25 subjects will be screened to obtain 18-20 subjects who complete all PK assessments. Dropouts will be replaced.

Cohort 2: Approximately 115 subjects will be screened to randomize approximately 90 subjects. Each clinical site will not randomize more than a maximum of 8-10 subjects without prior consent from the Sponsor.

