4.7 REPLACEMENT OF SUBJECTS

Approximately 25 subjects will be screened for Cohort 1 to ensure that subjects enter the study and complete all PK assessments; participants who discontinue prior to completion of all study-related procedures may be replaced. Approximately 115 subjects will be screened for Cohort 2 to randomize approximately 90 subjects into the T + M Period; randomized subjects will not be replaced.

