10. STATISTICS

10.1 DETERMINATION OF SAMPLE SIZE

No formal hypothesis tests are planned for the PK endpoints studied in Cohort 1. Thus, the sample size for Cohort 1 is based on practical considerations including the expected availability of appropriate subjects. The PK data from Cohort 1 will be used in combination with PBPK models that are being developed using robust data from adults and from existing PBPK models for the concomitant medications. In this way, the data from ZX008-1504 will be leveraged with existing PK information on fenfluramine, stiripentol, clobazam and valproate acid to confirm the expectations derived from the mechanism-based PBPK models. Analysis of the data in this way allows for the confirmation of the appropriateness of the extension of the PBPK model from adults to children and a robust assessment of the potential for a drug-drug interaction between ZX008 and stiripentol while limiting exposure to a smaller number of patients. The 18-20 subjects targeted for the PK phase of the study is expected to be sufficient to allow for the extension of the PK information gained in the ongoing PK study in adults and existing PBPK models to pediatric patients with Dravet syndrome.

The sample size for Cohort 2 is based on results from Study 1, the randomized, placebo-controlled study in subjects with Dravet syndrome sponsored by Zogenix (Lagae 2017). The standard deviation (SD) of the percentage change in seizure frequency from baseline to the end of study (Day 99) was 50% for the 0.8 mg/kg/day group and 69% for the 0.2 mg/kg/day. For the sample size calculation for Cohort 2, the SD is assumed to be intermediate between the SDs observed in the high and low dose groups in Study 1. Assuming an SD of 58, and using a two-sided test at the $\alpha=0.05$ significance level, a sample size of 45 subjects per treatment group affords 90% power to detect a difference in mean change in seizure frequency from baseline of 40 percentage points. Thus, the total sample size for Cohort 2 is planned to be approximately 90 subjects (45 per arm).

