6.9 CHANGES TO METHODS PLANNED IN THE PROTOCOL

- Protocol states that safety data will be summarized separately for the titration and maintenance periods as well as for the combined T+M period. Instead safety will be summarized only for the combined T+M..
- Protocol states that subjects in the safety population will be summarized by the treatment actually received. However, safety data will be presented by randomized treatment group except where noted otherwise.
- Protocol states that a sensitivity analysis for the primary efficacy endpoint will be conducted by adding a factor indicating whether a subject had a change in prescribed

dose or type of concomitant AED medication during the T+M Period, however this is not planned to be conducted.

- The protocol stated that the longest interval between convulsive seizures will be analyzed using a log-rank test. Instead groups will be compared with a Wilcoxon test.
- Responder analyses – The protocol included a $\geq 40\%$ response analysis as one of the key secondary endpoints. It was decided to not include this in the hierarchical testing of secondary endpoints.
- An analysis of the percentage of subjects who achieve a 25% reduction in seizures was added.,
- The Protocol states that the BRIEF rating scale will be used to evaluate cognition in children aged 2-18. The BRIEF-P will be used for children aged 2-4, and the BRIEF will evaluate children aged 5-18. The Protocol further states that the cognition subscale of the BRIEF will be used to evaluate cognition. The BRIEF and the BRIEF-P will be used to evaluate cognition.
- The Protocol states the Clinical Global Impression ratings by Investigator and Caregiver are exploratory endpoints. They are secondary endpoints.
- The protocol states the sample size is approximately 70 randomized subjects. As explained in [Section 6.1.10](#), the sample size was adjusted to approximately 80 randomized subjects based on data from the completed study of Epidiolex in Dravet syndrome.

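### The SAP plans 80 subjects and says the protocol plans about 70, but the supplied protocol plans about 90, and the SAP's list of departures does not show this difference

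*SAP*

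**What the plan says.** **SAP, final 25 June 2018.** Section 6.1.10 begins with 35 per arm at SD 50 from two stiripentol trials. It raises the SD to 55 after the Epidiolex results and concludes that "the sample size for the current trial was increased from 35 to 40 subjects per treatment arm for a total of 80 subjects". It says this number "affords 90% power to detect a difference in mean change from baseline of 40 percentage points with 55% SD". Section 6.9, which lists departures from the protocol, says: "The protocol states the sample size is approximately 70 randomized subjects". It then reports that "the sample size was adjusted to approximately 80 randomized subjects".

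**Protocol, Amendment 3.3 (US/CAN), 2 February 2018.** Section 10.1 assumes an SD of 58 and states that "a sample size of 45 subjects per treatment group affords 90% power to detect a difference in mean change in seizure frequency" of 40 percentage points. The source is the sponsor's own Study 1, whose SDs were 50 (0.8 mg/kg/day) and 69 (0.2 mg/kg/day): "the SD is assumed to be intermediate between the SDs observed in the high and low dose groups in Study 1". Section 3.2 gives the same target, "Approximately 115 subjects will be screened to randomize approximately 90 subjects", and so do Section 4.7 ("Approximately 115 subjects will be screened for Cohort 2 to randomize approximately 90 subjects into the T + M Period") and the synopsis.

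**Analysis scale.** SAP 6.3.1.1 makes log T+M seizure frequency the response of the primary ANCOVA, with log baseline frequency as covariate. SAP 6.3.1.2 uses percentage change as the response in a supplementary ANCOVA.

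**The concern.** The two documents give different planned numbers, SDs and source data for the same confirmatory comparison. Section 6.9 is where a reader looks for departures from the protocol, and it describes a protocol figure that is not in the supplied protocol's operative text. There, 70 survives only as replaced text in the Appendix 10 summary of changes. That history is used here only to explain where the 70 probably came from; the finding rests on current SAP text against current protocol text.

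At stake are the accuracy of the record and, if recruitment followed the SAP, some power. A reader could also take the 90% in 6.1.10 as the power of the primary test, which neither document calculates.

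**Working it through.** **Inputs.** Difference 40 points, two-sided alpha 0.05, target power 90% and 1:1 allocation (both documents). SD 50, then 55 (SAP 6.1.10); SD 58 (protocol 10.1). Neither sample-size section states a dropout allowance, so none is applied.

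**Formulas (normal approximation).** With z-values 1.960 and 1.2816, which sum to 3.2415:

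- n per arm = 2 × (SD × 3.2415 / 40)²
- power = Φ(40 / (SD × √(2/n)) − 1.960)

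The noncentral t with 2n − 2 degrees of freedom is the cross-check.

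**Step 1: the SAP's figure.** 2 × (55 × 3.2415 / 40)² = 39.73, so 40 per arm (41 by t). It reproduces.

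**Step 2: the protocol's figure.** 2 × (58 × 3.2415 / 40)² = 44.18, so 45 per arm (46 by t). It reproduces.

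**Step 3: power.**

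| n per arm | SD | Power, normal | Power, noncentral t |
|---|---|---|---|
| 35 (SAP starting point) | 50 | 91.7% | 91.0% |
| 40 (SAP) | 55 | 90.2% | 89.5% |
| 45 (protocol) | 58 | 90.5% | 89.9% |
| 40 (SAP n, protocol SD) | 58 | 87.0% | 86.1% |

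For the last row: 58 × √(2/40) = 12.97; 40 / 12.97 = 3.084; 3.084 − 1.960 = 1.124; Φ(1.124) = 0.870.

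**Step 4: detectable difference.** With 40 per arm at SD 58, 90% power needs 12.97 × 3.2415 = 42.0 points (42.6 by t) rather than 40.

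**Step 5: what SAP 6.9 discloses.** Declared change: 80 − 70 = +10 subjects. Difference from the supplied protocol: 80 − 90 = −10 subjects. Section 6.9 mentions neither 90, nor SD 58, nor Study 1.

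**Step 6: is only this bullet out of date?** No. Section 6.9 also attributes a log-rank test and a key secondary 40% responder endpoint to the protocol, and calls the 25% responder analysis an addition. The supplied protocol already has the Wilcoxon test (10.5.1.2), only the 50% endpoint as key secondary responder analysis (2.2), and the 25% analysis (2.3). The pattern fits a list written against earlier protocol text and not refreshed.

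**Step 7: scale.** The SDs and the 40 points refer to percentage change in seizure frequency. Power for the log-frequency ANCOVA needs a log-scale residual SD and an assumed treatment ratio; neither document gives them.

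**The case against.** The strongest reply is that little depends on the planned number. No interim analysis is planned, and no analysis population, model or step of the testing hierarchy uses it. The supplied protocol states about 90 consistently, and nothing in the SAP tells sites to stop at 80. This stands, and it limits the weight of the point.

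Second, only the US/CAN version of Amendment 3.3 is available, while Cohort 2 also recruits in France, Germany, the Netherlands, the United Kingdom and Spain. The SAP may follow a version not seen here. This also stands, so the mismatch is established against the supplied version only. Nothing suggests a deliberate or concealed departure.

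Third, the 86–87% is an unadjusted two-sample figure on the scale said not to describe the primary test, and baseline adjustment could recover some power. As an illustration, an assumed baseline–outcome correlation of 0.3 to 0.4, which neither document supplies, would bring 40 per arm at SD 58 to about 89–91% (noncentral t). That is a fair caution against reading 86–87% as the power of the planned model. It does not make the figure unsuitable for comparing the documents, because both 90% claims are two-sample figures on that same scale.

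Fourth, the scale point is separate from the mismatch and would remain if the SAP copied protocol 10.1, since protocol 10.5.1.1 defines the primary endpoint as change in mean convulsive seizure frequency. Percentage change is also summarised with the primary endpoint and, cut at 50%, is the first key secondary. All true; the scale point is subordinate, but one sentence resolves it.

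**Conclusion.** The concern holds. The SAP and the supplied protocol disagree on planned total (80 against about 90), SD (55 against 58) and source data, and SAP 6.9 reports a 70-to-80 change instead of the 90-versus-80 difference. Neither calculation contains an arithmetic error. If enrolment stopped at 80 and the SD were 58, power for 40 points would be 86.1–87.0%, about 3.5 to 4 points below that of 45 per arm (89.9–90.5%). Type I error and the analysis methods are unaffected.

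These figures assume a two-sample comparison of percentage change, a common SD and no dropout. They say nothing about the power of the log-frequency primary test. The point should be corrected, but it does not threaten the trial's inference.

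**What to change.** - Revise SAP 6.1.10 and the sample-size bullet in 6.9 to match protocol 10.1: about 90 subjects, 45 per arm, SD 58, Study 1.
- If the SAP follows another protocol version, name it. State the 90-versus-80 difference, the reason for it, and the 86–87% power of 40 per arm at SD 58, on the same two-sample percentage-change basis.
- Add a sentence saying that the 90% refers to a two-sample comparison of percentage change, not to the ANCOVA on log seizure frequency.
- Optional: if the sponsor has a log-scale residual SD from Study 1, add power for the primary ANCOVA and give the assumed treatment ratio.
- Housekeeping, with no effect on any analysis: update the 6.9 bullets on the log-rank test, the 40% responder endpoint and the 25% responder analysis.

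The cost is SAP wording only: no patients beyond the protocol's plan and no change to any analysis. Keeping 80 means acknowledging the lower power at the protocol's SD.

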6.2 SUBJECT CHARACTERISTICS

6.2.1 Disposition

Subject disposition will be presented per treatment group and overall.

For subjects enrolled but not randomized to treatment and for the reasons for not being randomized, the denominator used to calculate the percentage will be the number of enrolled subjects. For all other calculations the denominator will be the number of subjects randomized.

Completion and discontinuation data for all randomized subjects will be listed and sorted by treatment and site.

6.2.2 Protocol Deviations

Major protocol deviations will be summarized showing number and percent by treatment and overall based on the SAF. Major protocol deviations are those that have the potential to impact patient safety or affect data integrity. Major protocol deviations may be grouped into different important clinical categories such as

- Violation of inclusion/exclusion criteria
- Violation of randomization inclusion criteria
- Time schedule deviations of IMP
- Non-compliance regarding intake of IMP
- Inappropriate intake of concomitant medication
- Missing essential data
- Subject not discontinued as per protocol
- Other non-compliance

Multiple deviations can occur in the same subject and thus a subject may be counted in more than 1 deviation category.

Major protocol deviations will be presented in a subject data listing for all enrolled population, sorted by treatment and site.

6.2.3 Demographics and Baseline Characteristics

Subject demographics and baseline characteristics will be summarized descriptively per treatment group and overall, for the SAF and mITT populations.

6.2.3.1 *Subject Demographics*

The following demographic characteristics will be summarized:

- Age at screening [years]
- Categorical age as <6 years and ≥ 6 years.
- Sex
- Race
- Ethnicity
- Height [m]
- Weight [kg]
- BMI [kg/m^2]

All subject demographics data will be listed for the enrolled population.

6.2.3.2 *Other Baseline Characteristics*

Epilepsy genotype panel data will be descriptively summarized as per data type (categorical). Additional analyses of genetic data may be prepared in a separate report.

The primary genotype mutation for each subject will be listed for the safety population.

6.2.4 Treatment Exposure and Compliance

6.2.4.1 *Treatment Exposure*

Exposure will be summarized for the safety population.

Duration of exposure to treatment (i.e., time on treatment in days) will be calculated per subject as the number of days with IMP intake during the study and will be summarized using descriptive statistics (mean, standard deviation, median, and range) for the safety population. The per subject duration of exposure will be calculated as follows:

Date of last IMP administration – Date of first IMP intake + 1

The duration of exposure summary statistics will be presented by treatment group for the combined Titration, Maintenance and Taper/Transition periods. Also, the exposure subject data listing will be presented.

6.2.4.2 *Compliance*

Compliance will be summarized for the SAF and mITT.

Study medication is to be administered twice daily, and compliance is recorded in the eDiary as full (both doses), partial (less than full daily dose) or missed (both doses) each day. From this, compliance will be calculated by assuming that a missed dose=0% of dose consumed, partial=50% of dose consumed, and full=100% of dose consumed. For each subject, a daily compliance score will be thus obtained.

Compliance will be summarized for the SAF population over the course of T+M and Maintenance only, reported by treatment group.

6.2.5 Prior and Concomitant Medications and Therapies

Medications (collected on the prior/concomitant medication eCRF pages) will be coded using the World Health Organization Drug Dictionary (WHO-DD). The following algorithm will be used to define prior and concomitant:

Concomitant medications will be defined as those medications that were initiated after study drug administration or those that were ongoing at the time of study drug administration.

The medication will be assumed to be prior medication if it cannot be definitively shown that the medication did not start or continue during the double-blind treatment period.

If the start date or stop date of a medication is partially missing, the date will be compared as far as possible with the date of the start of administration of study drug. The following approach will be taken:

- If the start date of medication is complete and occurs on or after the day of the first dose, the medication will be assumed concomitant. If the start date occurs prior to the first dose date but the end date is on or after the first dose date or the medication is recorded as ongoing, the medication will be considered concomitant.
- If the start day is missing but the start month and year are complete, a medication will only be excluded as being concomitant if the start month/year is before the month/year of study drug administration and if the stop date (either full date, month and year if missing day, or year if missing month and day) is before study drug administration.
- If the start day and month are missing but the start year is complete, a medication will only be excluded as concomitant if the start year is before the year of study drug administration and if the stop date (either full date, month and year if missing day, or year if missing month and day) is before study drug administration.

- If the start date is completely missing and the stop date is prior to first dose or completely missing, the medication will be assumed to be a prior medication.

Medications will be summarized by treatment and overall for prior and concomitant medications by Anatomical Therapeutic Chemical (ATC) classification and preferred therapeutic Term (Level 2: pharmacological or therapeutic subgroup and Level 3: chemical or therapeutic or pharmacological subgroup). For each medication the number and percentage of subjects will be displayed.

Summary tables will be presented for SAF population.

All prior and concomitant medications/treatments will be listed for the SAF population.

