6.2.6 Prior and Concomitant Antiepileptic Treatment

Treatments (collected on the prior/concomitant antiepileptic treatment eCRF page) will be coded using the World Health Organization Drug Dictionary (WHO-DD).

Prior and concomitant antiepileptic will be defined and analyzed for the SAF similar to concomitant medications as described in [section 6.2.5](#).

All prior and concomitant antiepileptic treatments will be listed for the SAF population.

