8. APPENDICES

 APPENDIX 1: List of Tables, Figures, and Listings

Table/ Figure/ Listing	Number	Table Header
	14.1	Demographic data and other baseline characteristics
	14.1.1	Subject disposition
Table	14.1.1.1b	Overall Subject Disposition – All Enrolled Subjects
Table	14.1.1.2b	Major Protocol Deviations – Safety Population
Table	14.1.1.3b	Study Populations
	14.1.2	Demographic and other baseline characteristics
Table	14.1.2.1b	Demographic and Baseline Characteristics – Safety Population
Table	14.1.2.2b	Demographic and Baseline Characteristics – mITT Population
	14.1.3	Medical history
Table	14.1.3.1b	Medical History– Safety Population
	14.1.4	Prior and concomitant medication/treatment
Table	14.1.4.1b	Prior Medications and Therapies/Treatments – Safety Population
Table	14.1.4.2b	Concomitant Medications and Therapies/Treatments – Safety Population
Table	14.1.4.3b	Prior Antiepileptic Treatment – Safety Population
Table	14.1.4.4.1b	Concomitant Antiepileptic Treatment – Safety Population
Table	14.1.4.4.2b	Number of Subjects by Number of Concomitant Antiepileptic Treatments – Safety Population
	14.1.5	Treatment Exposure and compliance
Table	14.1.5.1b	Duration of Treatment Exposure – Safety Population
Table	14.1.5.2b	Compliance to IMP Intake – Safety Population
	14.2	Efficacy, pharmacokinetics, and pharmacodynamics
	14.2.1	Efficacy – ZX008 vs Placebo
Table	14.2.1.1.1b	Convulsive Seizure Frequency per 28 Days: Summary Statistics – mITT Population
Table	14.2.1.1.2b	Convulsive Seizure Frequency per 28 Days: Summary Statistics by Age Group – mITT Population
Table	14.2.1.2b	Convulsive Seizure Frequency per 28 Days : Parametric Analysis – mITT Population
Table	14.2.1.3b	Convulsive Seizure Frequency per 28 Days : Nonparametric Analysis – mITT Population
Table	14.2.1.4b	Percentage Change in Convulsive Seizure Frequency per 28 Days: Parametric Analysis – mITT Population

Table	14.2.1.5b	Percentage Change in Convulsive Seizure Frequency per 28 Days: Nonparametric Analysis – mITT Population
Table	14.2.1.6b	Mean Convulsive Seizure Frequency – Exploratory Efficacy Analysis of Subjects who are SCN1A Mutation Positive – mITT Population
Table	14.2.1.7b	Convulsive Seizure Frequency per 28 Days: Parametric Analysis – PP Population
Table	14.2.1.8b	Convulsive Seizure Frequency per 28 Days: Nonparametric Analysis – PP Population
Table	14.2.1.9b	Percentage Change in Convulsive Seizure Frequency per 28 Days: Parametric Analysis - PP Population

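### The SAP's date rule for medications contradicts its own definition of concomitant: an antiepileptic still being taken, with start and stop dates both completely missing, is classed as prior

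*SAP*

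**What the plan says.** SAP 6.2.5 defines concomitant medications as those begun after study drug administration, together with "those that were ongoing at the time of study drug administration". A default sentence follows: "The medication will be assumed to be prior medication if it cannot be definitively shown that the medication did not start or continue" during double-blind treatment. Four bullets then deal with dates.

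- **First bullet.** A complete start date on or after first dose means concomitant. If the start is before first dose but "the end date is on or after the first dose date or the medication is recorded as ongoing, the medication will be considered concomitant".
- **Second and third bullets.** With the start day missing, or day and month missing, the drug leaves the concomitant class only if the known part of the start date and the stop date both fall before study drug.
- **Fourth bullet.** With the start date completely missing, and a stop date that "is prior to first dose or completely missing, the medication will be assumed to be a prior medication".

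SAP 6.2.6 carries this over: "Prior and concomitant antiepileptic will be defined and analyzed for the SAF similar to concomitant medications". SAP Appendix 1 lists the outputs that depend on it, including Table 14.1.4.4.1b (concomitant antiepileptic treatment) and Table 14.1.4.4.2b, "Number of Subjects by Number of Concomitant Antiepileptic Treatments".

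Protocol 5.7 regards every medication taken after the first administration of study drug as concomitant. SAP 6.9, which lists departures from the protocol, declares none on this point.

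**The concern.** Cohort 2 tests ZX008 added to stiripentol with clobazam, valproate or both. Protocol 4.1 (criterion 7) requires that background to be stable before screening, and Protocol 5.7 requires it to continue unchanged. These drugs should therefore be ongoing at first dose and normally have no stop date. A rule that treats the absence of a stop date as grounds for prior works against the drugs the report most needs to show as concomitant.

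The two antiepileptic tables describe that background by arm. A record sent the wrong way would understate a subject's number of concomitant antiepileptics and could show a subject as not on stiripentol while taking it. SAP 6.9 also drops the sensitivity analysis for changes in antiepileptic medication, so the descriptive tables carry more of the account of background therapy.

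**Working it through.** No arithmetic applies; the rules can be traced case by case. Take an antiepileptic that is still being taken at first dose, has no stop date and is recorded as ongoing. Vary only what is known of the start date.

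| Start date known | Rule reached | Class |
|---|---|---|
| Complete, before first dose | First bullet, through the ongoing record | Concomitant |
| Month and year | Second bullet: no stop date before dosing | Concomitant |
| Year only | Third bullet: no stop date before dosing | Concomitant |
| Nothing | Fourth bullet: start and stop both completely missing | **Prior** |

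The drug and the subject's exposure are the same in every row. Losing the start year reverses the class, and the last row contradicts the definition at the head of the section. The ongoing record is named only in the first bullet, for a start known to precede first dose.

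The default sentence has the same fault. It assigns prior "if it cannot be definitively shown that the medication did not start or continue during the double-blind treatment period". Being unable to rule out use during treatment is a reason to call a drug concomitant, and the second and third bullets use it that way. Read literally, the sentence would even make prior a drug with no start date and a stop date after first dose. No bullet covers that drug, and the definition makes it concomitant.

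The SAP resolves the parallel question for adverse events the other way. Under SAP 6.1.7, when an end date is completely missing, ongoing status is examined first, and if the ongoing flag is also missing the event is taken to be still present. The medication rule has no such step.

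**The case against.** The strongest reply is that the general definition governs. It covers drugs ongoing at study drug administration, Protocol 5.7 agrees, and the first bullet shows that ongoing status is recorded. The second sentence of that bullet does not expressly require a complete start date. For stiripentol, clobazam and valproate, a start before first dose is known from eligibility, which requires a stable dose for at least 4 weeks before screening. A programmer could reasonably class a record flagged as ongoing as concomitant. That is a fair competing reading, so the wrong result is not certain. But the fourth bullet is the only one that names a completely missing start date, and it says prior. Two programmers could follow the same text and reach different tables.

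Four further points stand and limit the consequence:

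- A start year is often recoverable even for a drug begun long ago, and Protocol 9.2 provides for electronic checks and data queries.
- A misclassified record would move to Table 14.1.4.3b (prior antiepileptic treatment) and would still appear in Listing 16.2.4.4b.
- Background therapy has other evidence: the entry criterion, and plasma antiepileptic samples at Visits 3, 6, 8 and 12, listed in 16.2.10.1b.
- A subject shown without stiripentol in a trial that requires it would be a visible anomaly.

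**Conclusion.** SAP 6.2.5 is wrong as written and contradicts itself, within narrow limits. The fault needs a start date missing down to the year, a stop date that is also missing, and a programmer who follows the fourth bullet or the default sentence rather than the definition. Its effect is on descriptive safety-population tables: 14.1.4.4.1b and 14.1.4.4.2b, and 14.1.4.2b for other medications.

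Four stronger readings are tempting but not supported:

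- **Any missing start date triggers it.** It does not; with the year known, a drug with no stop date stays concomitant.
- **Many subjects would be miscounted.** For a subject on three antiepileptics, if a share p of records lacked any start date, independently of one another, the chance of at least one affected record would be 1 − (1 − p)³: 3%, 14% and 27% at assumed p of 1%, 5% and 10%. The documents give no p, and some subjects may be on stiripentol plus only one of the other two drugs. These figures illustrate the formula; they do not estimate the undercount.
- **Efficacy results are at risk.** The primary ANCOVA (SAP 6.3.1.1), the responder model (6.3.2.1) and the Wilcoxon test (6.3.2.3) do not use the classification. Per-protocol exclusions for antiepileptic changes come from the review of protocol deviations, not from this date rule.
- **A drug added during treatment would be hidden.** By the letter of the rule it could be, if both dates were completely missing. But concomitant medications are recorded at every on-treatment visit, so a new drug without even a start year is unlikely.

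This is a correction worth making because it is cheap and the text gives a wrong answer when followed. It does not threaten the trial's conclusions.

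**What to change.** In SAP 6.2.5:

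1. Replace the fourth bullet. If the start date is completely missing, the medication is prior only if its stop date is before first dose. It is concomitant if the stop date is on or after first dose, if the stop date is missing, or if the drug is recorded as ongoing.
2. Reverse the default sentence, so that a medication is assumed concomitant unless it is shown to have stopped before first dose.

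SAP 6.2.6 then inherits the corrected rule without further change, and the section agrees with its own definition, its other bullets and Protocol 5.7.

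The cost is two sentences and one line of derivation code, with no effect on design, alpha or the efficacy models. The downside is that a drug which ended before dosing but has no dates recorded may be counted as concomitant. That matches the direction the second and third bullets already take. A count of antiepileptic records with no start year, taken before unblinding, would show whether the change affects any table.
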